#### SARS-CoV-2 Infection:

- SARS-CoV-2 infection is defined in participants with SARS-CoV-2 negative at Baseline:
  - bAb level against SARS-CoV-2 nucleocapsid protein negative at Day 1 that becomes positive (as measured by Roche Elecsys) post Baseline, OR
  - Positive RT-PCR post Baseline

#### 7.3.2 Surveillance for COVID-19 Symptoms

While Part 2 is still blinded for any age group, COVID-19 surveillance will be conducted for all participants enrolled in the study.

Once the trial is unblinded for all age groups and thus no placebo comparator group is available going forward, COVID-19 surveillance will be discontinued, and COVID-19 cases will be reported under standard AE reporting per SoA only.

[figure not shown]
While Part 2 is still blinded for any age group, surveillance for COVID-19 symptoms will be conducted via biweekly telephone calls or eDiary prompts as specified in [Section 7.1.1](#) and [Figure 2](#); starting after participant enrollment and continuing throughout the study.

If there is no response to an eDiary prompt for 2 days, the study site staff will contact the study participant by telephone.

According to the CDC, as of 22 Dec 2020 ([CDC 2020c](#)), patients with COVID-19 have reported a wide range of symptoms ranging from mild symptoms to severe illness. Throughout the study while Part 2 for any age group is still blinded, to survey for COVID-19, the following pre-specified symptoms that meet the criteria for suspicion of COVID-19 will be elicited weekly from the participant, and the presence of any one of these symptoms (in the absence of an alternative diagnosis) lasting at least 48 hours (except for fever and/or respiratory symptoms) will result in the study site staff arranging an illness visit to collect a nasal swab for SARS-CoV-2 within 72 hours.

- Fever (temperature  $\geq 38^{\circ}\text{C}/\geq 100.4^{\circ}\text{F}$ ) or chills (of any duration, including  $\leq 48$  hours)
- Shortness of breath or difficulty breathing (of any duration, including  $\leq 48$  hours)
- Cough (of any duration, including  $\leq 48$  hours)
- Fatigue
- Muscle or body aches
- Headache
- New loss of taste or smell
- Sore throat
- Congestion or runny nose
- Abdominal pain
- Nausea or vomiting
- Diarrhea
- Poor appetite/poor feeding

**Figure 2: Surveillance for COVID-19 Symptoms and the Corresponding Clinical Data Pathways**

Abbreviations: COVID-19 = coronavirus disease 2019, HCP = healthcare practitioner, RT-PCR = reverse transcriptase polymerase chain reaction, SARS-CoV-2 = severe acute respiratory syndrome coronavirus 2.

It is important to note that some of the symptoms of COVID-19 overlap with solicited systemic ARs that are expected after vaccination with mRNA-1273 (eg, myalgia, headache, fever, and chills). During the first 7 days after vaccination, when these solicited ARs are common, investigators should use their clinical judgment to decide if a nasal swab should be collected. The collection of a nasal swab prior to the first dose on Day 1, prior to the second dose on Day 29, and then at all subsequent study visits (Day 43 [if visit is applicable], Day 57, Day 209, and Day 394) can help ensure that cases of COVID-19 are not overlooked. If the participant decides to receive the optional booster dose, nasal swabs should be collected as described in [Table 15](#).

Any study participant who reports respiratory symptoms during the 7-day period after vaccination without an alternative diagnosis should be evaluated for COVID-19.

For children with febrile illnesses, if an alternative diagnosis is identified (eg, positive urine culture, streptococcal pharyngitis, cellulitis), the investigator may decide to omit the illness visit. Identification of an alternative viral agent (such as respiratory syncytial virus or influenza by rapid testing) does not satisfy this requirement, as co-infections with SARS-CoV-2 may occur.

An investigator may elect to omit the illness visit if standard of care testing prior to the illness visit reveals a negative COVID-19 nucleic acid amplification test performed at a Clinical Laboratory Improvement Amendments (CLIA)-certified or CLIA-waived laboratory and the principal investigator can obtain a copy of the negative test. Home testing kits cannot be used to satisfy this testing requirement. Standard of care evaluation of household contacts that reveals a negative COVID-19 is not sufficient to omit an illness visit in the study participant.

During the course of the study when Part 2 for any age group is still blinded participants with symptoms of COVID-19 will be asked to return within 72 hours or as soon as possible to the study site or trained staff from the study site will conduct a home visit as soon as possible to collect a nasal swab sample (for RT-PCR) for evaluation of COVID-19. Both study site visits and home visits are referred to as illness visits ([Section 7.1.5](#)). Additionally, a convalescent visit may be scheduled approximately 28 days (+7 days) after diagnosis ([Section 7.3.3](#)) if there are any doubts about the initial diagnosis (at the discretion of the investigator). At this visit, a blood sample will be collected for potential immunologic assessment of SARS-CoV-2 infection.

Once the trial is unblinded for all age groups and thus no placebo comparator group is available going forward, illness visits for COVID-19 symptoms or exposures and convalescent visits will no longer be required.

Cases are defined as participants meeting clinical criteria based both on symptoms for COVID-19 and on RT-PCR detection of SARS-CoV-2 from samples collected within 72 hours of the study participant reporting symptoms meeting the definition of COVID-19. Participants who are hospitalized for COVID-19 without the opportunity for a clinic or home visit will also be considered cases, assuming that the symptomology criteria for COVID-19 are met and a respiratory sample is positive for SARS-CoV-2 by RT-PCR at a certified laboratory.

Investigators are encouraged to try to obtain a respiratory sample during the course of hospitalization or immediately after hospital discharge as an unscheduled visit for submission to the study central laboratory, if feasible. The investigator should determine if the criteria for severe COVID-19 have been met.

Severe COVID-19 is defined in [Section 7.3.1](#).

All clinical findings will be recorded in the eCRF. While COVID-19 surveillance is ongoing, all confirmed cases of symptomatic COVID-19 will be captured as MAAEs, along with relevant concomitant medications and details about severity, seriousness, and outcome, and will be reported immediately to the Sponsor or designee ([Section 7.4.4](#)). Once COVID-19 surveillance is discontinued, COVID-19 cases will be reported as per standard AE reporting (only if medically attended, SAEs or leading to discontinuation from study or vaccination).

### **7.3.3 Follow-up/Convalescent Period After Diagnosis with COVID-19**

Any confirmed symptomatic COVID-19 occurring in a participant will be captured as an MAAE along with relevant concomitant medications and details about severity, seriousness, and outcome. Additionally, a convalescent visit may be scheduled approximately 28 days (+ 7 days) after diagnosis if there are any doubts about the initial diagnosis (at the discretion of the PI). At this visit, a blood sample for potential immunologic assessment of SARS-CoV-2 infection will be collected (see the SoAs [[Section 10.1](#)]). The investigator should determine if the criteria for severe COVID-19 have been met. If the participant is hospitalized, study site personnel will try to obtain medical records and SARS-CoV-2 diagnostic results. If the participant is later discharged from the hospital during the 28-day period following diagnosis of COVID-19, the study site personnel will arrange for a resumption of the protocol schedule.

Children hospitalized with possible or confirmed MIS-C may also have the same convalescent visit scheduled approximately 28 days (+7 days) after onset of hospitalization at the Investigator's discretion. At this visit, a blood sample for potential immunologic assessment of SARS-CoV-2 infection will be collected (see the SoAs [[Section 10.1](#)]).

Once the trial is unblinded for all age groups and thus no placebo comparator group is available going forward, convalescent visits will no longer be required.

## **7.4 Safety Definitions and Related Procedures**

### **7.4.1 Adverse Event**

An AE is defined as any untoward medical occurrence associated with the use of a drug in humans, whether or not considered drug related.

#### **Events Meeting the Adverse Event Definition**

- Exacerbation of a chronic or intermittent pre-existing condition including either an increase in frequency and/or intensity of the condition.
- New conditions detected or diagnosed after the first dose of IP even though they may have been present before the start of the study.

### Events NOT Meeting the Adverse Event Definition

- Medical or surgical procedure (eg, endoscopy, appendectomy): the condition that leads to the procedure should be the AE.
- Situations in which an untoward medical occurrence did not occur (social and/or convenience admission to a hospital).
- Planned procedures (eg, tonsillectomy or pressure-equalization tubes) that occur during the study period but were planned prior to enrollment will not be considered AE unless complications arise.

An AR is any AE for which there is a reasonable possibility that the vaccine caused the AE ([Section 7.4.9](#)). For the purposes of IND safety reporting, “reasonable possibility” means that there is evidence to suggest a causal relationship between the vaccine and the AE.

An unsolicited AE is any AE reported by the participant that is not specified as a solicited AR in the protocol or is specified as a solicited AR but starts outside the protocol-defined period for reporting solicited ARs (ie, the day of each dose of injection and the 6 days after the day of dosing).

#### 7.4.2 Serious Adverse Events

An AE (including an AR) is considered an SAE if, in the view of either the investigator or Sponsor, it results in any of the following outcomes:

- **Death**  
A death that occurs during the study or that comes to the attention of the investigator during the protocol-defined follow-up period must be reported to the Sponsor, whether or not it is considered related to the IP.
- **Is life-threatening**  
An AE is considered life-threatening if, in the view of either the investigator or the Sponsor, its occurrence places the participant at immediate risk of death. It does not include an AE that, had it occurred in a more severe form, might have caused death.
- **Inpatient hospitalization or prolongation of existing hospitalization**  
In general, inpatient hospitalization indicates the participant was admitted to the hospital or emergency ward for at least one overnight stay for treatment that would not have been appropriate in the physician’s office or outpatient setting. The hospital or emergency ward admission should be considered an SAE regardless of whether opinions differ as to the necessity of the admission. Complications that occur during inpatient hospitalization will be recorded as AEs; however, if a complication/AE prolongs hospitalization or

otherwise fulfills SAE criteria, the complication/AE will be recorded as a separate SAE.

Note: 24-hour observation admissions, typically used to extend the period of observation from an emergency department or urgent care visit, will not be considered inpatient hospitalization unless they are converted to hospital admission after the 24 hours of observation have expired.

- **Persistent or significant incapacity or substantial disruption of the ability to conduct normal life functions**

This definition is not intended to include experiences of relatively minor medical significance such as uncomplicated headache, nausea/vomiting, diarrhea, influenza, and accidental trauma (eg, sprained ankle) that may interfere with or prevent everyday life functions but do not constitute a substantial disruption.

- **Congenital anomaly or birth defect**

- **Medically important event**

Medical judgment should be exercised in deciding whether SAE reporting is appropriate in other situations, such as important medical events that may not be immediately life-threatening or result in death or hospitalization but that jeopardize the participant or require medical or surgical intervention to prevent one of the other outcomes listed in the above definition. These events should usually be considered serious. Examples of such medical events include allergic bronchospasm requiring intensive treatment in an emergency room or at home, blood dyscrasias or convulsions that do not result in inpatient hospitalization, or the development of drug dependency or drug abuse.

#### **7.4.3 Solicited Adverse Reactions**

The term “reactogenicity” refers to the occurrence and intensity of selected signs and symptoms (ARs) that occur after IP injection. The eDiary will solicit daily participant reporting of ARs using a structured checklist ([Section 7.1.1](#)). Participant’s parent(s)/LAR(s) will record such occurrences in an eDiary on the day of each dose of injection and for the 6 days after the day of dosing.

Severity grading of reactogenicity will occur automatically based on participant entry into the eDiary according to the grading scales presented in [Table 8](#) and [Table 9](#), modified from the Toxicity Grading Scale for Healthy Adult and Adolescent Volunteers Enrolled in Preventative Vaccine Clinical Trials ([DHHS 2007](#)).

If a solicited local or systemic AR continues beyond Day 7 after vaccination, the participant’s parent(s)/LAR(s) will be prompted to capture details of the solicited local or systemic AR in the eDiary until it resolves or the next IP injection occurs, whichever occurs first. Capture of details of ARs in the eDiary should not exceed 28 days after each vaccination. Adverse reactions

recorded in the eDiary beyond Day 7 should be reviewed by the study site staff either during the next scheduled telephone call or at the next study site visit. All solicited ARs (local and systemic) will be considered related to the IP.

After booster doses with mRNA-1273.214, local or systemic ARs will only be reported if they are medically attended, considered serious or lead to discontinuation from the study. No eDiaries will be used after booster doses with mRNA-1273.214.

**Table 8:      Solicited Adverse Reactions and Grades: Age 37 Months to < 12 years**

Reaction	Grade 0	Grade 1	Grade 2	Grade 3	Grade 4
Injection site pain	None	Does not interfere with activity	Interferes with activity	Prevents daily activity	Requires emergency room visit  or hospitalization
Injection site erythema (redness)	< 25 mm/ < 2.5 cm	25-50 mm/ 2.5-5 cm	51-100 mm/ 5.1-10 cm	> 100 mm/ > 10 cm	Necrosis or exfoliative dermatitis
Injection site swelling/induration (hardness)	< 25 mm/ < 2.5 cm	25-50 mm/ 2.5-5 cm	51-100 mm/ 5.1-10 cm	> 100 mm/ > 10 cm	Necrosis
Axillary (underarm) swelling or tenderness ipsilateral to the side of injection	None	No interference with activity	Some interference with activity	Prevents daily activity	Emergency room visit  or hospitalization
Headache	None	No interference with activity	Some interference with activity	Significant; Prevents daily activity	Requires emergency room visit  or hospitalization
Fatigue	None	No interference with activity	Some interference with activity	Significant; prevents daily activity	Requires emergency room visit  or hospitalization
Myalgia (muscle aches all over body)	None	No interference with activity	Some interference with activity	Significant; prevents daily activity	Requires emergency room visit  or hospitalization
Arthralgia (joint aches in several joints)	None	No interference with activity	Some interference with activity	Significant; prevents daily activity	Requires emergency room visit  or hospitalization
Nausea/vomiting	None	No interference	Some interference	Prevents daily activity,	Requires emergency room visit  or

Reaction	Grade 0	Grade 1	Grade 2	Grade 3	Grade 4 
		with activity or 1-2 episodes/ 24 hours	with activity or > 2 episodes/ 24 hours		hospitalization for hypotensive shock
Chills	None	No interference with activity	Some interference with activity not requiring medical intervention	Prevents daily activity and requires medical intervention	Requires emergency room visit  or hospitalization
Fever	< 38.0°C < 100.4° F	38.0-38.4°C 100.4-101.1°F	38.5-38.9°C 101.2-102.0°F	39.0-40.0°C 102.1-104.0°F	> 40.0°C > 104.0°F

 Age at time of enrollment determines the scale to be used.

 Grading for Grade 4 events per investigator assessment (with exception of fever).

 Emergency room visit includes urgent care visit.

Source: Guidance for industry – Toxicity Grading Scale for Healthy Adult and Adolescent Volunteers Enrolled in Preventative Vaccine Clinical Trials ([DHHS 2007](#)).

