### **5.3.2 Administration of Study Vaccine**

In Part 1 and Part 2, each participant will receive 2 doses of IP by IM injection approximately 28 days apart (Day 1 and Day 29). Part 1 and Part 2 participants who did not previously receive any booster doses will be offered a booster dose of IP by IM injection at least 3 months after Dose 2.

For Part 3, each participant will receive 3 doses of IP by IM injections approximately 28 days apart for the 2 primary doses of the primary series followed by a third dose at least 3 months and up to 5 months after receipt of the second dose of the primary series (Day 1, Day 29, and Day 149/BD-Day 1). The IM injections will be administered into the deltoid muscle or anterolateral thigh (per investigator's discretion), according to their assigned regimen and according to the procedures specified in the mRNA-1273-P204 Pharmacy Manual.

At each visit when IP is administered, participants will be monitored for a minimum of 30 minutes after administration. Assessments will include body temperature measurements (oral preferred for participants  $> 4$  years of age, tympanic preferred for participants  $\leq 4$  years of age, but other methods acceptable in context of COVID-19 precautions) and monitoring for local or systemic reactions.

Eligibility for the subsequent dose of IP will be determined by following the criteria outlined in [Section 6](#).

The study sites will be appropriately staffed with individuals with basic cardiopulmonary resuscitation training/certification. Either on-site resuscitation equipment and personnel or appropriate protocols for the rapid transport of participants to a resuscitation area or facility are required.

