### 7.1.1 Use of Electronic Diaries

At the time of consent, participants' parent(s)/LAR(s) must confirm they will be willing to complete an eDiary using either an application downloaded to their smartphone or using a device that is provided at the time of enrollment. Before enrollment on Day 1, participants' parent(s)/LAR(s) will be instructed to download the eDiary application or will be provided an eDiary device to record solicited ARs ([Section 7.4.3](#)) on Day 1. Based on availability, smartphone devices may be provided to those participants' parent(s)/LAR(s) who do not have their own device to use for eDiary activities.

At each injection visit, participants' parent(s)/LAR(s) will be instructed (Day 1) or reminded (Day 29, BD-Day 1, if applicable) on thermometer (oral/tympanic) usage to measure body temperature, ruler usage to measure injection site erythema and swelling/induration (hardness), and assessment for localized axillary swelling or tenderness on the same side as the injection arm/thigh.

At each injection visit, participants' parent(s)/LAR(s) will record data into the eDiary starting approximately 30 minutes after injection under the supervision of the study site staff to ensure successful entry of assessments. The study site staff will perform any retraining as necessary. Participants' parent(s)/LAR(s) will continue to record data in the eDiary after they leave the study site, preferably in the evening and at the same time each day, on the day of injection and for 6 days following injection.

Participants' parent(s)/LAR(s) will record the following data in the eDiary:

- Solicited local and systemic reactogenicity ARs, as defined in [Section 7.4.3](#), that occur on the day of each vaccine administration and during the 7 days after vaccine administration (ie, the day of injection and 6 subsequent days). If a solicited local or systemic AR continues beyond Day 7 after vaccination, the participant's parent(s)/LAR(s) will be prompted to capture details of the solicited local or systemic AR in the eDiary until it resolves or the next IP injection occurs, whichever occurs first. Capture of details of ARs in the eDiary should not exceed 28 days after each vaccination. Adverse reactions recorded in the eDiary beyond Day 7 should be reviewed by the study site staff either during the next scheduled telephone call or at the next study site visit.

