**Table 9: Solicited Adverse Reactions and Grades: Age 6 Months to ≤ 36 Months**

Reaction	Grade 0	Grade 1	Grade 2	Grade 3	Grade 4 
Local Reaction					
Injection site pain/tenderness	None	Mild discomfort to touch or some pain but no interference with normal daily activities	Cries when limb is moved/refuses to move limb or pain interferes with normal daily activities	Significant pain at rest or pain prevents normal daily activities	Requires emergency room visit  or hospitalization
Injection site erythema (redness)	< 5 mm/ < 0.5 cm	5-20 mm/ 0.5-2.0 cm	> 20-50 mm > 2.0-5.0 cm	> 50 mm/ > 5 cm	Necrosis or exfoliative dermatitis
Injection site swelling/induration (hardness)	< 5 mm/ < 0.5 cm	5-20 mm/ 0.5-2.0 cm	> 20-50 mm > 2.0-5.0 cm	> 50 mm/ > 5 cm	Necrosis

Reaction	Grade 0	Grade 1	Grade 2	Grade 3	Grade 4 
Groin or underarm swelling or tenderness ipsilateral to the side of injection	None	Some swelling or tenderness but no interference with normal daily activities	Swelling or tenderness that interferes with normal daily activities	Swelling or tenderness that prevents normal daily activities	Emergency room visit  or hospitalization
Systemic Reaction					
Fever	< 38.0°C	38.0-38.4°C 100.4-101.1°F	38.5-39.5°C 101.2-103.1°F	39.6-40.0°C 103.2-104.0°F	> 40.0°C > 104.0°F
Irritability/crying	None	Lasting < 1 hour or easily consolable	Lasting 1-3 hours or requiring increased attention	Lasting > 3 hours or inconsolable	Requires emergency room visit  or hospitalization
Sleepiness	None	Sleepier than usual or less interested in surroundings	Not interested in surroundings or sleeps through meals	Sleeps most of the time, hard to arouse	Inability to arouse
Loss of appetite	None	Eating less than normal for 1-2 feeds/meals	Missed 1-2 feeds/ meals completely	Missed > 2 feeds/meals completely or refuses most feeds/meals	Requires emergency room visit  or hospitalization

 Age at time of enrollment determines the scale to be used.

 Grading for Grade 4 events per investigator assessment (with exception of fever).

 Emergency room visit includes urgent care visit.

Source: Guidance for industry – Toxicity Grading Scale for Healthy Adult and Adolescent Volunteers Enrolled in Preventative Vaccine Clinical Trials ([DHHS 2007](#)).

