#### **7.4.13 Method of Detecting AEs and SAEs**

Electronic diaries have specifically been designed for this study by the Sponsor. The diaries will include prelisted AEs (solicited ARs) and intensity scales; they will also include blank space for the recording of information on other AEs (unsolicited AEs) and concomitant medications/vaccinations.

The investigator is responsible for the documentation of AEs regardless of treatment group or suspected causal relationship to IP. For all AEs, the investigator must pursue and obtain information adequate to determine the outcome of the AE and to assess whether the AE meets the criteria for classification as an SAE requiring immediate notification to the Sponsor or its designated representative.

Care will be taken not to introduce bias when detecting AEs and/or SAEs. Open-ended and nonleading verbal questioning of the participant and participant's parent(s)/LAR(s) is the preferred method to inquire about the occurrence of AE.

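### For children of 37 months and older the diary solicits only armpit swelling, although thigh injection is allowed at any age, so a groin node reaction after a thigh injection is not counted as a solicited reaction

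*Protocol*

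**What the plan says.** **Injection site.** Section 5.3.2 states: "The IM injections will be administered into the deltoid muscle or anterolateral thigh". The choice is left to the investigator, and no age limit is attached.

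**Diary item, 37 months to <12 years (Section 7.4.3, Table 8).** The only regional node item is "Axillary (underarm) swelling or tenderness ipsilateral to the side of injection".

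**Diary item, 6 to 36 months (Section 7.4.3, Table 9).** The corresponding item is "Groin or underarm swelling or tenderness ipsilateral to the side of injection".

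**Choice of table.** A footnote to both tables says: "Age at time of enrollment determines the scale to be used". The injection site plays no part.

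**Instruction to parents (Section 7.1.1).** At each injection visit parents are instructed or reminded on "assessment for localized axillary swelling or tenderness on the same side as the injection arm/thigh". This applies to all ages.

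**Everything else.** Section 7.4.1 says: "An unsolicited AE is any AE reported by the participant that is not specified as a solicited AR in the protocol". Unsolicited AEs are collected for 28 days after each injection (Section 7.1), and the diary has free-text space for them (Section 7.4.13).

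**The concern.** Sections 5.3.2 and 7.1.1 both foresee thigh injections, and Table 9 shows that the groin was recognised as a relevant region. Table 8 does not carry this over to children of 37 months and older. A child on Table 8 who is injected in the thigh stays in the denominator for the node item, but has no item on which a groin reaction can score.

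Solicited local reactions within 7 days are a primary safety endpoint (Section 2, Table 2). They are summarised by grade and age group (Section 8.5.2), and they feed pause rule 4 (Section 6.4, Table 5). At stake are the completeness of one solicited item and the comparability of its rate across age groups and injection sites.

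There is a second inconsistency for younger children: parents using Table 9 are trained under Section 7.1.1 to look only at the armpit, while their diary asks about the groin as well.

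**Working it through.** The protocol states no figure on this point, so there is none to reproduce. The check is a comparison of sections, followed by a simple sensitivity calculation.

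**1. Can a groin reaction score as solicited?**

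| Child's table | Injection site | Relevant region | Solicited item in the table? | Covered by the 7.1.1 instruction? |
|---|---|---|---|---|
| Table 9 (6 to 36 months) | Arm | Armpit | Yes | Yes |
| Table 9 (6 to 36 months) | Thigh | Groin | Yes | No |
| Table 8 (37 months to <12 years) | Arm | Armpit | Yes | Yes |
| Table 8 (37 months to <12 years) | Thigh | Groin | **No** | **No** |

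**2. What changes when the event is unsolicited instead?**

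- *Prompting:* solicited items are asked daily from a checklist (Section 7.4.3). An unsolicited event depends on someone raising it.
- *Grading:* on Table 8, node swelling that prevents daily activity is Grade 3, assigned from the diary entry. For unsolicited AEs, Section 7.4.8 defines severe as preventing daily activity and also needing intensive therapy. The same event can therefore receive a lower grade.
- *Causality:* all solicited reactions are treated as related (Section 7.4.3). Unsolicited AEs need an investigator's judgement (Section 7.4.9).
- *Pause rules:* rule 4 counts solicited local reactions of Grade 3 or higher, with a threshold of at least 2 participants and at least 5% of those dosed in an age group. A groin event does not enter it. Rule 6 covers unsolicited AEs of Grade 3 or higher with no reasonable cause other than vaccination, with a threshold of at least 2 participants and at least 5% of those enrolled in an age group.

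**3. Size for children on Table 8.**

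Inputs, none of which the protocol gives:

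- *f*, the share of injections given in the thigh: assumed 0% to 50%.
- *r*, the true rate of regional node swelling or tenderness: assumed equal after arm and thigh injection, with 10% and 20% used for illustration.
- No groin event is entered under the armpit item.

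Formula: solicited rate observed = r × (1 − f). The relative understatement is f.

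- r = 10%: f = 0% gives 10.0%; f = 5% gives 10% × 0.95 = 9.5%; f = 20% gives 10% × 0.80 = 8.0%; f = 50% gives 10% × 0.50 = 5.0%.
- r = 20%: f = 5% gives 20% × 0.95 = 19%; f = 30% gives 20% × 0.70 = 14%.

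**4. The 2 to <6 year group.** Children enrolled at up to 36 months use Table 9 and the others use Table 8. If w is the share of the group on Table 8, with r the same on both tables, the group's relative understatement is w × f. This is smaller than f, but the pooled rate then combines two definitions.

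**5. The composite.** The rate of any solicited local reaction is affected less than the single item. A child with a groin reaction is lost from it only if no other solicited local reaction was recorded.

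**The case against.** **The event is not lost.** A reader might infer that groin reactions after thigh injection cannot be captured at all. The protocol does not support that. They can be written in the diary's free-text space, elicited by the standard question at every visit or call (Section 7.4.7), and raised when staff review the diary with parents 7 days after injection (Section 7.1.1). Unsolicited AEs are then tabulated by preferred term (Section 8.5.2). What is lost is daily prompting, automatic grading and the solicited count. Section 7.1.1 also lets sites enter a verbally reported solicited reaction on the solicited form, but that route is doubtful here because groin swelling is not a solicited reaction on Table 8.

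**The event is not misfiled.** Under Section 7.4.1, recording it as unsolicited is the correct filing. The fault lies in the item, not in the coding.

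**Pause oversight is not removed.** Rule 6 uses the same numbers as rule 4, with a denominator worded as enrolled rather than dosed. This stands in part: the stricter definition of severe in Section 7.4.8 makes rule 6 a weaker backstop.

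**The effect may be nil.** The thigh share, the true rate and its equality between sites are all assumed. The booster schedules (footnote 2 of Tables 15 and 19) speak only of examining the arm that receives the injection, which hints that thigh use may be rare in those phases. This stands: no fixed bias can be asserted.

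**Little diary use remains.** There is no diary after mRNA-1273.214 boosters (Section 7.4.3), and the cross-over schedule in Table 13 lists no diary activation. Solicited diaries remain mainly for any outstanding Part 3 doses (Table 17). This stands and limits the prospective benefit.

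**No hypothesis test depends on the item.** This is also true, since the safety analysis is descriptive.

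**Conclusion.** The inconsistency is real but minor. Table 8 and the Section 7.1.1 instruction do not match the sites allowed in Section 5.3.2, and Section 7.1.1 does not match Table 9. For a child on Table 8 injected in the thigh, a groin node reaction falls outside the solicited local reactions and pause rule 4, and appears, if reported, as an unsolicited AE that may count under rule 6.

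The solicited node-reaction rate is understated by the thigh share in this age range, and by less in the 2 to <6 year group as a whole. The calculated rates show how the effect scales. They rest on an assumed thigh share and an assumed true rate, equal at both sites, and they do not estimate what happened in this trial. If no child on Table 8 was injected in the thigh, the rate is not affected. A flat statement that the reported rate is too low would go beyond the document. What stands regardless of the thigh share is that the 2 to <6 year group pools two item definitions and that the passages contradict each other.

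**What to change.** **Wording.** Use the Table 9 item, "Groin or underarm swelling or tenderness ipsilateral to the side of injection", in Table 8, and change the parent instruction in Section 7.1.1 to name the groin as well as the armpit. Apply this to any remaining solicited diary use, such as Part 3.

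**Data already collected.** Where the injection site was recorded, report the node item by site for children on Table 8. Footnote the number with groin swelling or tenderness recorded as an unsolicited AE within 7 days of a thigh injection. Section 5.4 asks for the date and time of each dose and does not mention site, so first check whether site is available. If it is not, state in the report that the item covers only the armpit for children on Table 8. In either case, note beside the 2 to <6 year results that two item definitions are pooled.

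**Cost.** One diary label, one line of instruction and, where the site is known, one extra breakdown. No new procedure is needed for the wording change. The drawback is a change of item wording part-way through the study, which should be footnoted wherever results before and after it are combined.
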